11.1.6. Pharmacokinetic Variables

Pharmacokinetic variables will be analyzed separately. The analysis is described in a separate document.

11.1.7. Multicenter Data

Randomization will be stratified by center group as detailed in the Section 13.7.2 of the protocol.

The analyses of the primary and secondary endpoints of this trial will adjust for possible effects of the variable center by including it as covariate in the analyses.

11.1.8. Handling of Multiple Comparisons

Unless otherwise specified, all statistical tests will be conducted against a two-sided alternative hypothesis, employing a significance level of 0.05. The primary and secondary endpoints of efficacy will be tested in a hierarchy, so as to preserve the nominal significance levels:

1. Primary
2. Incidence of surgery
3. Time to complete eschar removal
4. Blood loss.

11.1.9. Interim analysis

No interim analyses will be performed.

11.1.10. Stratification

The following factors are used to stratify the study design:

A. Total TBSA % per patient

A1: Total TBSA <=15%

A2: Total TBSA >15%

B. Overall depth per patient

B1: All TWs are full thickness;

B2: Mixed TWs – full thickness and deep partial thickness

B3: All TWs are deep partial thickness.

C. Center Group, to address possible differences in SOC procedures between sites (if any), to allow comparison of the results within group of centers and to reduce the likelihood of a group of centers including patients in only one arm of the study (5 groups of centers were formed based on similarity of SOC practice).

These factors are accounted for in the analyses of the primary and secondary endpoints by including them as adjusting variables.

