9.1. Sample Size

The following sample size calculations are based on the consideration of the primary and two secondary endpoints for this study.

Estimated effects of NexoBrid from study MW2004-11-02 were used to design the study with adequate statistical power using the following steps.

- (a) Sample size calculations were based on study MW2004-11-02;
- (b) The effect of NexoBrid versus standard of care was estimated together with the standard error of the estimate; the effect of NexoBrid versus gel was estimated based on study MW2002-04-01, previous phase II study, which included 35 patients treated with gel vehicle.

The size of the effect to be detected in this study, MW2010-03-02, was taken as the previous estimate decreased by half its standard error, in order to use a conservative value.

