9.3.1. Summary of sample size

Although the maximum sample size from the above calculations is a total of 121 patients (65 in the NexoBrid group, 13 in the Gel vehicle group and 43 in the SOC group (to match NexoBrid numbers)), we propose entering larger numbers to provide an extra margin of assurance in achieving positive results on the efficacy outcomes, and adequate information on safety outcomes to allow better benefit vs. risk assessment.

Therefore, we plan a study with total sample size of 175 patients; 75 (NexoBrid) + 75 (SOC) + 25 (Gel Vehicle).

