procedure (surgical/non-surgical) to the subset containing patients with complete data in those variables for both treatment groups separately. Impute the missing entries of the incomplete data sets $m = 25$ times as follows: Draw a set of regression coefficient from their sampling distribution obtained from fitting the respective linear models outlined above (a different distribution for the regression coefficients will be obtained in the different treatment groups). With these sampled coefficients calculate the predicted blood loss values for the procedures with missing blood loss using the covariate information. To these predicted blood loss values add the realizations of a normally distributed random variable with zero mean and standard deviation equal to the residual standard deviation from the linear model fitted to the complete data set. The random seeds for these 25 imputations will be (11468, 11469, 11470, ..., 11492). On the imputed datasets calculate the blood loss on a patient level.

3. Analysis: Analyze each of the m complete data sets with a t-test or the Mann-Whitney test according to the test result in step 1. This step results in m estimates of the effect and m estimates of the standard deviation.
4. Pooling: Integrate the m analysis results into a final result with the SAS procedure PROC MIANALYZE according to Rubin's combination rules for multiple imputation to obtain the final estimates of mean and variance [28].

For the additional analysis of blood loss which treats the whole eschar removal process as one continuous procedure (see section 7.3.2.2) the multiple imputation will be performed on a patient level. The procedure can be described as follows:

1. Test for normality: The Shapiro-Wilk test will be performed on the dataset of non-missing values in each treatment group. The result of these tests will determine the type of the analysis on the imputed data sets (step 3.). If the normal distribution hypothesis is not rejected at the 5% significance level in either group, then differences in distribution between NexoBrid and SOC will be tested using a t-test. If the normal distribution hypothesis is rejected either in the NexoBrid group or in the SOC group, then the differences in distribution between the treatment groups will be tested using a Mann-Whitney test.

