2. Imputation: Fit a linear regression model with target variable blood loss on a patient level (as computed in Section 10.3.3.3) and dependent variables wound area, depth of wound (categorized as described in Section 11.1.10) and course of debridement procedure (as defined in Section 10.3.3.3.5) to the subset containing patients with complete data in those variables for both treatment groups separately. Impute the missing entries of the incomplete data sets $m = 25$ times as follows: Draw a set of

regression coefficient from their sampling distribution obtained from fitting the respective linear models outlined above (a different distribution for the regression coefficients will be obtained in the different treatment groups). With these sampled coefficients calculate the predicted blood loss values for the procedures with missing blood loss using the covariate information. To this predicted blood loss values add the realization of a normally distributed random variable with zero mean and standard deviation equal to the residual standard deviation from the linear model fitted to the complete data set. The random seeds for these 25 imputations will be (12467, 12468, 12469, ..., 12491). On the imputed datasets calculate the blood loss on a patient level.

3. Analysis: Analyze each of the m complete data sets with a t-test or the Mann-Whitney test according to the test result in step 1. This step results in m estimates of the effect and m estimates of the standard deviation.
4. Pooling: Integrate the m analysis results into a final result with the SAS procedure PROC MIANALYZE according to Rubin's combination rules for multiple imputation to obtain the final estimates of mean and variance [28].

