11.1.3. Secondary Efficacy variables

The secondary endpoints will be analyzed as described below and will compare efficacy in the NexoBrid group with the SOC group. Missing data will be handled by the methods described in Section 10.1. All secondary endpoints will be analyzed using the FAS. Sensitivity analyses will include analyzing the endpoints using the PP as analysis population.

11.1.3.1. *Incidence of surgical excision*

This is a binary yes/no variable and the proportion of patients who need excision for eschar removal will be compared using logistic regression. The explanatory variables in the model will include treatment, and the following variables: overall TW depth (all TWs full thickness, mixed TWs, all TWs deep partial thickness), “Total %TBSA per patient” and number of TWs (1, 2, ≥3). The odds ratio of requiring surgery for NexoBrid versus SOC will be estimated from the model, as well as 95% confidence intervals and the level of statistical significance. The results

will be displayed as shown in Table 6 and Table 7. Bar plots will be shown for the proportions of patients who needed excision for eschar removal.

If numerically possible, as a supportive analysis, the variable treatment center will be added into the logistic regression model and the analysis repeated.

As a sensitivity analysis, the logistic regression outlined above will be repeated using the PP as analysis population.

If any of the baseline factors, gender, age, percent SPT area (the area of SPT as a percentage of the total area of all TWs, classified as <25% or ≥25%), time from injury to randomization or number of TWs (1, 2, ≥3) are found to be significantly different between the treatment groups, then the factor will be included as an extra adjusting covariate in the logistic regression model described above as additional analysis.

As supportive analysis, the incidence of surgical excision for eschar removal will be compared between NexoBrid and Gel Vehicle using the same explanatory variables as in the main analysis of this endpoint.

A further supportive analysis will repeat the analysis (NexoBrid versus SOC) as described above, but on a wound level. I.e. a mixed logistic regression model with explanatory variables treatment, TW depth, %TBSA per wound and number of TWs and a random effect for patient will be performed.

11.1.3.2. *Time to complete eschar removal*

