As an additional analysis, time to complete eschar removal will be compared between NexoBrid and Gel Vehicle using the same explanatory variables as for the main analysis of this endpoint.

11.1.3.3. *Blood loss*

In Section 10.3.3.3 two blood loss estimates are defined. Analyses with both blood loss estimates will be conducted. However, some missing values are expected. The analysis with less missing values will be regarded as more reliable and is therefore considered the main analysis. The other analysis is considered supportive. Both analyses will be conducted as follows:

The measure of blood loss defined in Section 10.3.3.3 will be computed for each patient, and the distribution in the NexoBrid group will be compared with that in the SOC group. Means, standard deviations, medians, and interquartile ranges will be calculated and presented as in Table 4. Furthermore, the blood loss will be described graphically by histograms. The normality of the data will be tested on each treatment group using the Shapiro-Wilk test. If the normal distribution hypothesis is not rejected at the 5% significance level in either group, then differences in distribution between NexoBrid and SOC will be tested using a t-test. If the normal distribution hypothesis is rejected either in the NexoBrid group or in the SOC group, then the

differences in distribution between the treatment groups will be tested using a Mann-Whitney test. The test results will be presented as in Table 7.

As sensitivity analysis, the procedure outlined above will be repeated using the PP instead of the FAS as analysis population.

Supportive analyses will include adjustments for the covariates overall TW depth (all TWs full thickness, mixed TWs, all TWs deep partial thickness), "Total %TBSA per patient", center group (as defined in Section 11.1.10), number of TWs (1, 2, ≥ 3) and number of debridement procedures. This will be done by including these variables in a regression model for blood loss together with treatment group.

If any of the baseline factors, gender, age, or percent SPT area (the area of SPT as a percentage of the total area of all TWs, classified as $<25\%$ or $\geq 25\%$), time from injury to randomization are found to be significantly different between the treatment groups, then the factor will be included as an extra adjusting covariate in a supportive analysis of blood loss (as described in the preceding paragraph).

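### Sections 11.1.7 and 11.1.10 claim adjustment for the stratification factors, but only one of the four main analyses uses all three, and the main blood-loss test uses none

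*SAP*

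**What the plan says.** Section 11.1.10 lists three stratification factors: total TBSA (two levels), overall depth (three levels) and centre group (five groups). It closes with "These factors are accounted for in the analyses of the primary and secondary endpoints by including them as adjusting variables". Section 11.1.7 says of centre alone that the primary and secondary analyses "will adjust for possible effects of the variable center by including it as covariate in the analyses". Neither section separates main from supportive analyses.

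The endpoint sections are more specific.

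- **Primary (11.1.2).** Fisher's exact test decides. Depth, TBSA and centre group each enter a separate supportive logistic model, if it can be fitted.
- **Excision (11.1.3.1).** The main logistic model has treatment, depth, TBSA and number of target wounds. For centre: "If numerically possible, as a supportive analysis, the variable treatment center will be added into the logistic regression model and the analysis repeated".
- **Time to eschar removal (11.1.3.2).** The Cox model, and the stratified Wilcoxon-Gehan fallback, include depth, TBSA, centre group and number of target wounds.
- **Blood loss (11.1.3.3).** A t-test or Mann-Whitney test decides. Adjustment comes later: "Supportive analyses will include adjustments for the covariates overall TW depth", with TBSA, centre group, number of target wounds and number of debridement procedures. The same section describes its main analysis as having no covariate adjustment.

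Sections 11.2.4.2 and 11.3.4.3 call the MVSS difference adjusted for imbalance in the stratification factors. Their model has depth, TBSA and number of target wounds, but not centre group.

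**The concern.** A reader of 11.1.7 and 11.1.10 would expect every confirmatory comparison to be adjusted for the stratification factors, and the trial report could repeat that claim for analyses that do not adjust.

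For the primary test the SAP gives its reason. For blood loss section 11.1.3.3 gives none, although the SAP treats these factors as prognostic. Section 7.1 stratifies because outcomes are expected to depend on burn area and depth. Section 10.1.1.3 counts wound area and depth among the main prognostic factors for blood loss, and its patient-level imputation model uses wound area with "depth of wound (categorized as described in Section 11.1.10) and course of debridement procedure". That depth variable is the stratification class itself.

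A test that ignores prognostic strata after stratified randomisation uses too large a standard error, so it is conservative and loses power. Blood loss was also not sized. Section 9.1 states: "The following sample size calculations are based on the consideration of the primary and two secondary endpoints for this study". The only cushion is the general increase in 9.3.1 from 121 to 175 patients (SOC from 43 to 75), where "we propose entering larger numbers to provide an extra margin of assurance in achieving positive results on the efficacy outcomes".

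**Working it through.** **Step 1. Count the factors in each main analysis.**

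| Endpoint (order in 11.1.8) | Main analysis | TBSA | Depth | Centre group | Used |
|---|---|---|---|---|---|
| 1. Complete eschar removal | Fisher's exact test | no | no | no | 0/3 |
| 2. Surgical excision | logistic regression | yes | yes | no | 2/3 |
| 3. Time to eschar removal | Cox, or stratified Wilcoxon-Gehan | yes | yes | yes | 3/3 |
| 4. Blood loss | t-test or Mann-Whitney | no | no | no | 0/3 |

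One of four matches 11.1.10.

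**Step 2. The plan's own figures.** There is none for blood loss. For the first two endpoints the SAP's sizes reproduce with unadjusted Fisher tests: 65 vs 13 at 0.5665 vs 0.10 gives 90.8% power, and 43 vs 43 at 0.24 vs 0.60 gives 90.4%. At the planned 75 vs 25 and 75 vs 75 the values are 99.5% and 99.4%. Power gives no reason to change those two analyses.

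**Step 3. Direction of the effect for blood loss.** Let R² be the share of variance explained by the strata (assumed). In the limit of exact balance within strata, an unadjusted t-test has actual two-sided alpha 2(1 - Φ(1.96/√(1 - R²))). If the adjusted test has 90% power, the unadjusted one has Φ(1.96 + 1.2816 - 1.96/√(1 - R²)).

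| R² | 1.96/√(1 - R²) | Actual alpha | Unadjusted power |
|---|---|---|---|
| 10% | 2.066 | 3.9% | 88% |
| 20% | 2.191 | 2.8% | 85% |
| 30% | 2.343 | 1.9% | 82% |
| 50% | 2.772 | 0.6% | 68% |

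The error is on the conservative side.

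**Step 4. Simulation of the SAP rule.**

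- From the SAP: N = 175, 3:3:1, 2 × 3 × 5 = 30 strata, NexoBrid vs SOC, Shapiro-Wilk per arm at 5% and then t-test or Mann-Whitney.
- Assumed: blocks of 7, TBSA split 70/30, depth 25/40/35, equal centre groups, effect 0.35 SD, R² shared equally by the three factors. For log-normal data, effect and R² are on the log scale.
- Comparator: rank ANCOVA on treatment and the three factors. Complete data, 4,000 replicates per cell.

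Power, SAP rule vs rank ANCOVA (%):

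| R² | Normal | Log-normal | Exponential errors | Change, points |
|---|---|---|---|---|
| 0 | 58.4 vs 56.5 | 55.9 vs 55.2 | 89.0 vs 88.5 | -2 to 0 |
| 5% | 57.5 vs 57.1 | 56.0 vs 57.1 | 83.2 vs 84.9 | 0 to 2 |
| 10% | 58.2 vs 59.0 | 53.4 vs 57.3 | 78.8 vs 84.0 | 1 to 5 |
| 20% | 58.4 vs 64.0 | 55.0 vs 63.7 | 72.0 vs 83.2 | 6 to 11 |
| 40% | 58.7 vs 75.8 | 54.5 vs 74.5 | 65.5 vs 87.2 | 17 to 22 |

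If only TBSA and depth matter, the gains are much the same (1 to 5, 7 to 11, 18 to 23 at 10, 20 and 40%). At 0.53 SD, where the SAP rule already has 89 to 93% on normal and log-normal data, they shrink to 0.8 to 1.6, 2.2 to 3.5 and 4.8 to 6.7. A smaller repeat (2,500 replicates per cell) agreed at R² 10 to 40%; at R² 0 it ranged from a gain of 0.2 to a loss of 3.3 points.

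**Step 5. Block size.** On log-normal data the SAP rule rejects a true null as follows.

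| Blocks of | R² 20% | R² 40% |
|---|---|---|
| 7 | 3.2% | 2.1% |
| 14 | 4.0% | 3.3% |
| 28 | 4.7 to 4.9% | 4.0 to 4.2% |

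Strata average 175/30 = 5.8 patients, so larger blocks seldom fill and balance is looser. The power gain hardly moves: about 2 to 5, 7 to 9 and 17 to 20 points at R² 10, 20 and 40% across the three block sizes.

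**Step 6. Missing values.** With 10% or 20% missing completely at random, 25 patient-level imputations and Rubin's rules (1,500 replicates per cell), a rank model with the strata gains 2 to 3, 5 to 7 and 12 to 16 points over one without, at R² 10, 20 and 40%. True-null rejection of the pooled rank ANCOVA is 4.1 to 5.9% on normal data and 1.6 to 3.7% on log-normal data. The imputation used TBSA group in place of wound area and left out the course of debridement. The procedure-level imputation was not simulated.

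**The case against.** The two general sentences speak of the analyses, not the main analyses, and every factor does appear in some planned analysis of every endpoint. On that reading they are loose rather than false. But several of those models are conditional, and for the primary endpoint the factors enter one at a time; neither section warns of this. The wording still needs correcting.

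An unadjusted two-sample test with adjusted supportive models is valid and prespecified, and blood loss is last in the hierarchy, so its loss of power blocks nothing else. The amendment summary for version 9 also records, in general terms, that analyses were limited on regulatory advice to the terms expected to matter most. That could explain sparse models, though it does not mention blood loss. The gain rests on an R² the SAP does not give: the imputation model shows that area and depth were thought predictive, not how strongly, and it omits centre. These points stand and limit the weight of the blood-loss change.

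A reader might infer three stronger claims that the documents do not support:

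- *The confirmatory tests are left open.* They are not: each endpoint section names its deciding test.
- *Type I error is inflated.* The direction is conservative.
- *The planned test has a known, markedly low true-null rate that adjustment would restore to 5%.* The rate depends on a block size this SAP does not state, and with missing values on skewed data the pooled rank ANCOVA is itself conservative.

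**Conclusion.** The general statements in 11.1.7 and 11.1.10 are wrong for three of the four main analyses, and this should be corrected whatever is decided about blood loss. The MVSS wording is a smaller instance, in stages the SAP calls exploratory.

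For blood loss the case for change is power alone. At 0.35 SD with complete data it ranges from a loss of about 2 points if the strata explain nothing to a gain of 17 to 22 if they explain 40% of the variance. Effect size and R² are assumptions. The SAP's own choice of stratification and imputation variables makes R² of zero unlikely but does not fix its value.

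**What to change.** 1. **Reword 11.1.7 and 11.1.10** to state, for each endpoint, which factors enter the main analysis and which are supportive only: primary none; excision depth and TBSA; time to eschar removal all three; blood loss as fixed in item 2. Write centre group throughout, in place of centre or treatment centre. Keep Fisher's test and the excision model.
2. **Before treatment codes are used, make the main blood-loss analysis a rank ANCOVA.** In each imputed data set, rank patient-level blood loss over NexoBrid and SOC and regress the ranks on treatment, TBSA group, depth and centre group. Leave out number of debridement procedures, which arises after randomisation. The treatment coefficient and its standard error fit the pooling step already planned: "Integrate the m analysis results into a final result with the SAS procedure PROC MIANALYZE". Set the complete-data degrees of freedom to the residual value, 150 - 9 = 141 if all 150 patients contribute. The imputation model can stay: adding centre group changed power by -1.1 to +2.5 points. Keep the unadjusted test as supportive.
3. **In 11.2.4.2 and 11.3.4.3**, say the MVSS difference is adjusted for depth, TBSA and number of target wounds, not for all stratification factors.

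Cost: no new data. The changes are to SAP text; whether the protocol also fixes the blood-loss test cannot be seen here. Item 2 can lose about 2 points of power if the strata are not prognostic. It gives a coefficient in rank units (the medians by arm already planned carry the clinical size), and its pooled inference can stay conservative on skewed data with missing values.

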11.1.11. Analysis of Subgroups

The following subgroup analyses were pre planned and will be conducted to explore efficacy and safety within certain pre-defined subgroups of the population. All analyses presented here are of exploratory nature.

11.1.11.1. Target wounds in the anatomical area of the hand

A subgroup analysis will be performed on the subgroup of target wounds that are found, at least partly, in the anatomical area of the hand. The primary and secondary endpoints will be analyzed while only taking wounds that are found, at least partly, in the anatomical area of the hand into account.

11.1.11.2. Patients with < 25% SPT area

Patients will be classified as having < 25 % or \geq 25% SPT area as a percentage of the area of all TWs.

For the subgroup of patients with < 25 % SPT area descriptive statistics (counts and percentages) of patients achieving complete eschar removal will be displayed for patients treated with NexoBrid or Gel Vehicle as shown in Table 5. The two groups will be compared using Fisher's exact test. The results will further be described by a bar plot (see Figure 2).

For the secondary endpoint "surgical excision performed" counts and percentages of patients needing surgical excision will be presented (see Table 5). The treatment groups will be compared using a chi square test (of Fisher's exact test in case of small expected cell counts).

The secondary endpoint "time to complete eschar removal" Kaplan-Meier estimates will be presented graphically and in a table (see Figure 3 and Table 8). Time to complete eschar removal will be compared between treatment groups by a log rank test.

For the secondary endpoint "blood loss" the number of subjects, number of missing values, means, standard deviations, medians, quartiles, minimums and maximums will be calculated

and presented as in Table 4. Furthermore, the blood loss will be described graphically by histograms (see Figure 1). Treatment groups will be compared using a t-test.

The safety endpoint “time to reach complete wound closure” will be analyzed by presenting Kaplan-Meier estimates graphically and in a table (see Figure 3 and Table 8). Time to complete wound closure will be compared between treatment groups by a log rank test.

11.1.11.3. *Patients with $\geq 25\%$ SPT area*

The same analysis as in Section 11.1.11.2 will be done but on the subgroup of patients with $\geq 25\%$ SPT area.

11.1.11.4. *Total TBSA $\leq 15\%$*

The same analysis as in Section 11.1.11.2 will be done but on the subgroup of patients with total TBSA $\leq 15\%$.

11.1.11.5. *Total TBSA $> 15\%$*

The same analysis as in Section 11.1.11.2 will be done but on the subgroup of patients with total TBSA $> 15\%$.

11.1.11.6. *All target wounds full thickness*

The same analysis as in Section 11.1.11.2 will be done but on the subgroup of patients with all target wounds classified as full thickness wounds.

11.1.11.7. *Mixed target wounds – full thickness and deep partial thickness*

The same analysis as in Section 11.1.11.2 will be done but on the subgroup of patients with mixed thickness target wounds (full thickness and deep partial thickness).

11.1.11.8. *All target wounds are deep partial thickness*

The same analysis as in Section 11.1.11.2 will be done but on the subgroup of patients with all target wounds classified as deep partial thickness wounds.

11.1.11.9. *Wounds that are entirely full thickness*

The same analysis as in Section 11.1.11.1 will be performed but on the subgroup of wounds that are entirely full thickness wounds.

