11.1.4.1. Safety Endpoint: Time to wound closure

This safety endpoint will be analyzed using the FAS. A sensitivity analysis will be done by repeating the analysis outlined below with the PP as analysis population.

Time to reach complete wound closure will be compared between the NexoBrid and SOC at a wound level using a method of survival analysis with clustered data that is based on appropriate assumptions. By "clustered data", we refer to the multiple target wounds that can occur in a patient. As stated in the protocol, a non-inferiority margin will be incorporated into the analysis that will represent a 7-day advantage to the SOC group. This will be done by adding 7 days to the wound closure times in the SOC group. After that, the proportional hazards assumption will be checked in the same way as in the analysis of the timely eschar removal endpoint. I.e. a marginal cox regression model with a robust sandwich estimator (see below for further details) will be performed including the variables treatment, TW depth (on a wound level), %TBSA (on a wound level) and number of TWs (1, 2, ≥ 3) as well as a variable

representing the interaction between time since randomization and treatment group. If the coefficient for this time variable is non-significant at the 5% significance level, then the proportional hazards assumption will be considered appropriate. In this case we will use a marginal Cox regression analysis with a robust sandwich estimator. If not, then we will use an accelerated failure time (AFT) model with shared frailty. Note that this deviates from the previously planned parametric frailty model implemented in the SAS procedure PHREG. The latter one assumes proportional hazards and is therefore not suitable here.

Either method can be implemented in SAS (see [33] for details). The marginal Cox regression model is implemented in the PHREG procedure and the robust variance option is implemented by specifying the COVS(AGGREGATE) option. This induces the use of the robust variance method of Binder et. al. [34]. The accelerated failure time model with shared frailty will be implemented using the following SAS-code:

```
PROC NLIN DATA=burn_data;
BOUNDS gamma>0;
linp = b0 + b1*treatment_group + b2*spt + b3*dpt + b4*ft + b5*tbsa +
b6*number_tw2+ b7*number_tw3 + b8*center2 + b9*center3 + b10*center4 +
b11*center5 + z;
alpha = exp(-linp);
G_t = 1/(1+alpha*time**gamma);
g = alpha*gamma*time**gamma/(1+alpha*time**gamma)**2;

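### The exploratory subgroup tests never compare the effect across levels, and the wound-closure subgroup test omits the 7-day margin and does not state its unit

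*SAP*

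**What the plan says.** SAP 11.1.11 introduces analyses that "will be conducted to explore efficacy and safety within certain pre-defined subgroups of the population" and adds: "All analyses presented here are of exploratory nature".

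11.1.11.2 sets one test per endpoint within a subgroup:
- complete eschar removal: Fisher's exact test;
- excision: chi-square or Fisher's test;
- time to eschar removal: log-rank test;
- blood loss: "Treatment groups will be compared using a t-test";
- wound closure: "Time to complete wound closure will be compared between treatment groups by a log rank test".

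11.1.11.3 to 11.1.11.8 repeat this by reference, typically in the form "The same analysis as in Section 11.1.11.2 will be done but on the subgroup of patients with" a given feature. That makes seven patient-level subgroups and five endpoints, or 7 × 5 = 35 tests.

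The main closure analysis in 11.1.4.1 is built differently. The arms are compared "at a wound level using a method of survival analysis with clustered data that is based on appropriate assumptions", and "a non-inferiority margin will be incorporated into the analysis that will represent a 7-day advantage to the SOC group". On how the margin enters: "This will be done by adding 7 days to the wound closure times in the SOC group". The model is a marginal Cox regression with robust variance, or a shared-frailty accelerated failure time (AFT) model if proportional hazards is rejected.

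**The concern.** Whether a factor changes the treatment effect is a question about the difference between levels. Separate p-values inside each level do not answer it, because they also depend on how many patients each level holds. The SAP's own summary of changes from protocol version 9 to 11 (Appendix 13.5.1, line 40) says that the entirely-full-thickness and SPT subgroups were added to test for effects of wound depth. The SPT pair is analysed only by within-level tests.

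Wound closure is the more important case. It is a safety endpoint on which the main analysis tries to exclude a 7-day disadvantage. A test of no difference asks something else. In a small subgroup it will often be non-significant whether or not such a delay exists.

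**Working it through.** **1. Is there any comparison across levels?** 11.1.11 contains none. The one related provision is in 11.1.3.2: for time to eschar removal, treatment interactions are examined for baseline factors found imbalanced. That list includes SPT share but not TBSA or depth. The interaction term exists only in the Cox branch.

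**2. The closure test against the main analysis**

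| | 11.1.4.1 (main) | 11.1.11.2 (subgroup) |
|---|---|---|
| Null hypothesis | NexoBrid no better than SOC plus 7 days | no difference |
| Unit | wound | not stated |
| Within-patient correlation | robust variance or frailty | not mentioned |

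10.3.4.1 defines complete-closure time per wound only. A patient-level censoring rule appears in 10.3.5.17, but for 100% closure. So the subgroup test either treats wounds as independent or uses an undefined variable.

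**3. The plan's own figures.** The SAP gives no figure for subgroups or closure. Its other sizes reproduce:
- excision, 0.24 v 0.60, Fisher, 43 per arm: power 90.4% (stated 90%);
- time to eschar removal: 4(1.96 + 1.28)²/1.23² = 27.75, so 28 events as stated.

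**4. How often do two levels disagree when the effect is the same in both?** With powers a and b, exactly one is significant with probability a(1 − b) + b(1 − a).
- *Assumed 90% overall power.* The standardised effect is 1.96 + 1.2816 = 3.242. Each half has power Φ(3.242/√2 − 1.96) = 0.630, so disagreement is 2 × 0.630 × 0.370 = 47%.
- *Excision at the enrolled 75 v 75.* Overall power is 99.4%. Halves of 37 and 38 per arm have 84.1% and 85.6%: 0.841 × 0.144 + 0.856 × 0.159 = 26%. A 75/25 split (56 and 19 per arm) has 96.4% and 53.5%: 0.964 × 0.465 + 0.535 × 0.036 = 47%.
- *Primary at the enrolled 75 v 25* (0.5665 v 0.10, Fisher): 24% for equal halves, 66% for 75/25.
- *Time to eschar removal*: 75 × (0.595 + 0.728) ≈ 99 events, giving about 2% and 14%.

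**5. What does a non-significant closure test show?** Assumptions, since the SAP gives no closure distribution: log-normal times, log-SD 0.5, median 25 to 35 days, one wound per patient, no censoring, 2,000 simulated trials. With a true 7-day delay:

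| Patients per arm | Plain log-rank non-significant |
|---|---|
| 10 | 80–88% |
| 20 | 73–85% |
| 37 | 57–74% |

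At 37 per arm, a log-rank test with SOC times shifted by 7 days wrongly claims non-inferiority in about 3% of trials.

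**6. If wounds are treated as independent.** With m wounds per patient and intraclass correlation ρ (neither is given), the design effect is 1 + (m − 1)ρ and the true size of a 5% test is 2[1 − Φ(1.96/√DEFF)].
- m = 1.5, ρ = 0.3: DEFF 1.15, size 6.8%.
- m = 3, ρ = 0.8: DEFF 2.6, size 22.4%.

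Simulation with varying wound counts at 37 patients per arm gave 7% and 26% at these two corners.

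**The case against.** The strongest reply is that nothing confirmatory rests on these tests. 11.1.11 labels them exploratory, formal testing is confined to the four-step hierarchy in 11.1.8, and the closure conclusion comes from the full-sample clustered analysis with the margin. The later-stage tests are called exploratory too (11.2.8, 11.3.8). All of that stands. A reader might infer that type I error control or the main safety conclusion is compromised; the document does not support this. Nor does it say that a non-significant subgroup result will be read as absence of harm.

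A reader might also infer that clustering is definitely ignored. The subgroup text names no unit, and a patient-level analysis would have no clustering. What can be shown is that the unit is unstated and that the patient-level time is undefined for this endpoint.

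The 47% for equal halves assumes exactly 90% power, and the trial enrols more than its calculations require. The figures at enrolled size are lower for equal halves on all three sized endpoints.

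The fixed t-test and the unadjusted excision and eschar-removal tests might be read as further errors. Simple methods are defensible in small exploratory subgroups, and that choice is a matter of preference.

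Finally, interactions have little power: with equal halves, 90% overall power and an effect difference as large as the overall effect, Φ(3.242/2 − 1.96) = 37%. The margin-shifted test is also weak: with no true delay and 37 per arm it claims non-inferiority in only about 23 to 44% of trials. Both are reasons to report intervals. Neither makes the planned tests informative about effect differences or delay.

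**Conclusion.** The point holds as one of interpretation and internal consistency in analyses that are exploratory by declaration. Apart from the conditional SPT interaction in 11.1.3.2, 11.1.11.2 to 11.1.11.8 cannot show whether the effect varies with SPT share, TBSA or depth. With a common effect at the planning values and enrolled size, differing significance would arise about 26% of the time for excision with equal halves and 47% with a 75/25 split. For time to eschar removal it would be much rarer.

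For closure, the subgroup test does not address the 7-day question, and its unit must be settled. The 57 to 74% and the 7 to 26% rest on assumed closure times, wound counts and correlations; the second range applies only if wounds are analysed as independent.

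**What to change.** Keep everything labelled exploratory and amend 11.1.11.2 to 11.1.11.8 as follows.

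- **Excision (logistic) and time to eschar removal (Cox, if proportional hazards holds):** add a treatment-by-factor term to the main model for SPT share, TBSA and depth in turn. Report level-specific estimates with 95% confidence intervals and one interaction p-value per factor.
- **Primary endpoint and blood loss:** the main tests are Fisher's test and a t-test or Mann-Whitney test, so there is no main model to extend. Report level-specific differences with intervals (exact for the primary), and an interaction only where estimable. With 25 Gel Vehicle patients and 0 of 35 successes in the earlier study, it may not be for the primary.
- **Wound closure:** replace the log-rank test with the clustered model of 11.1.4.1, with SOC times shifted by 7 days. Report the level-specific hazard ratio or AFT coefficient with its interval. Neither model yields a difference in days.
- **MVSS subgroups (11.2.11, 11.3.11):** replace the one-way analysis of variance with the NexoBrid minus SOC difference and its 95% interval, shown against the 1.9 used in the main analysis.

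The cost is SAP wording and some programming, with no new data or patients. Interaction estimates will be imprecise, and many subgroup intervals will be inconclusive.
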